## 2.4 | 3D analysis

Two STL files were obtained from each patient and, to allow for blinding, an external operator provided the STL files named with the patient reference number followed by the letter A (reference) or B (measured), keeping the correspondence code in an opaque sealed envelope until the end of the study. The files were imported into a reverse engineering software Geomagic Design X (3D Systems, Rock Hill, South Carolina) where they were cut to the zone of interest with the “Split” tool, removing unnecessary information and submitted to the “Healing Wizard” to reduce the number of distortions and small artifacts that could influence analysis. The generated datasets were then imported into the point-cloud inspection software Geomagic Control X (3D Systems).

Software validation was performed as previously reported and repeated five times per scan (60 repetitions in total) to check software reliability, after which, virtual sagittal planes were created to guide the standardization of the locations of interest—through the cervicalapical axis of each of the five structures (four teeth and one implant), frontal planes over the mesiodistal axis of the implant and the two adjacent teeth, three transversal planes parallel between them in the four teeth, one at the gingival zenith and two others apically from the first with 1 mm spacing between them, and in the implant at emergence profile base level which was defined with a horizontal plane in the most apical identifiable point of the customized emergence profile, mucosal zenith, and in the middle of them. The locations were determined by the intersection between the described planes with the superimposed scans and the linear differences obtained by the 3D analysis program. The amount of deviation between methods was obtained by calculating the root mean square (RMS) by previously established methods.

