To evaluate the trueness between conventional (reference) and digital (comparison) impression methods, RMS distances were determined on both the buccal and palatal sides of the teeth, at cervical, incisal and in the middle point between them in each tooth (Bc, Bm, Bi, Pc, Pm, and Pi) and in the respective soft tissues (Gbc, Gbm, Gbz, Gpz, Gpm, and Gpc), as shown in Figure 4A. In the interproximal area of the implant (mesial and distal sides, Mip and Dip), the same locations as in buccal/palatal were measured (Figure 4B). In total, 304 comparisons were performed in teeth's hard and soft tissues to assess trueness between methods.

To evaluate the soft tissue replication between methods in periimplant soft tissues, the locations were measured at emergence profile base level (epbl), at the zenith (z), and middle (m) on the different sides of the implant mucosa: the buccal of the buccal mucosa (Bbm), the palatine of the buccal mucosa (Pbm), the buccal of the palatine mucosa (Bpm), the palatine of the palatine mucosa (Ppm), and the mesial and distal mucosa (Mm and Dm, respectively) (Figure 4C,D), corresponding to 18 locations per patient, amounting to a total of 108

measurements. If the scans presented teeth with modifications, for prosthesis fabrication or distortions, the affected areas were not assessed.

For each location with the “3D Compare” tool an area of interest with at least 1 mm^2 was selected and used to measure the differences between methods, with three replicates performed per location. The analysis software automatically calculated RMS and the mean of the three replicates considered for statistical analysis.

For optimal 3D visualization, a colored map was created with negative (blue, showing the comparison scan going inwards) and positive values (red, going outwards), as shown in Figure 5. Specific parameters were set to the color scale, ranging from +1000 to -1000  $\mu\text{m}$  and the best results ranging between +100 and -100  $\mu\text{m}$ , highlighted in green. Values over or below the color scale's limits were presented in gray.

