## 2.5 | Statistical analysis

Although no studies employing this technique were found in the literature, from a study on direct and indirect techniques in CIIC22 we expected a mean difference of 1 mm. A statistical power analysis was performed to determine the number of patients with an equivalence study design. With an  $\alpha = .05$ , and a power of 0.80, the calculations revealed that at least six patients would be needed to be 95% sure that the limits of a two-sided 90% confidence interval would exclude a difference in means of more than 500  $\mu\text{m}$ .

Primary outcomes were defined as the variation in the RMS between the two methods in the hard (teeth) and soft (teeth and periimplant mucosa) tissues' measurements. Descriptive statistic (means and 95% confidence intervals) was performed on the studied parameters. Normality of distribution was tested by the Shapiro-Wilk Normality test and the Levene test was used to assess the equality of variance. According to the results, the nonparametric Mann-Whitney U and Kruskal-Wallis tests were used to compare RMS between methods in hard and soft tissues ( $\alpha = .05$ ). When performing multiple comparisons, the P-value was adjusted according to the Bonferroni Correction method.

Effect size between soft tissues' measurements (tooth vs implants) was calculated as Hedges'  $g$   $\pm$  95% confidence interval as a result of different sample sizes. Effect size was considered as small (<0.3), moderate (0.3–0.8), or large ( $\geq 0.8$ ) effect. The level of significance was set at .05. All calculations were carried out with statistical software (SPSS 25.0, SPSS Inc., Chicago, Illinois).

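### Section 2.5 applies independent-data tests, intervals and a two-sample Hedges' g to RMS values clustered in six patients, with no patient effect, pairing or stated unit of analysis; pooled intervals are probably too narrow

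*Combined protocol and SAP*

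**What the plan says.** Section 2.5 counts the sample in patients: "the calculations revealed that at least six patients would be needed". For the analysis it says "Descriptive statistic (means and 95% confidence intervals) was performed on the studied parameters", and then that "the nonparametric Mann-Whitney U and Kruskal-Wallis tests were used to compare RMS between methods in hard and soft tissues". The tooth-versus-implant effect size for soft tissue is Hedges' g with a "95% confidence interval as a result of different sample sizes". A Bonferroni correction is named for multiple comparisons.

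Section 2.4 describes the data. "Two STL files were obtained from each patient", and all locations are defined on the superimposed scans. Each patient contributes four teeth and one implant. The peri-implant values are described as "corresponding to 18 locations per patient, amounting to a total of 108", and the tooth comparisons number 304. Each location is measured three times, with "the mean of the three replicates considered for statistical analysis". Where teeth were modified or scans distorted, "the affected areas were not assessed".

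Neither section mentions a paired test, a patient effect, an adjustment for clustering or a summary per patient. Neither says whether patient, tooth or location is the unit of inference.

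**The concern.** Mann-Whitney U, Kruskal-Wallis, the ordinary confidence interval of a mean and the two-sample Hedges' g all treat each value as a separate piece of evidence. Here all values of a patient share one intraoral scan, one digitised stone model and one superimposition. An error in any of these would move many of that patient's values together, so positive within-patient correlation is plausible, although the documents do not quantify it.

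The primary outcomes are the hard- and soft-tissue RMS values, described by means and 95% intervals. If over a hundred correlated sites are counted as independent, agreement between the two methods will look more precise than six patients can support.

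A second ambiguity adds to this. The tests are said to compare the methods, yet each RMS value is already a deviation between the two methods. Which groups the tests compare is therefore unclear; only Hedges' g is labelled tooth versus implant.

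**Working it through.** **Number of patients.** 108 / 18 = 6. Independently, the software check used five repetitions per scan and 60 in total (section 2.4): 60 / 5 = 12 scans, and 12 / 2 = 6. Both agree with the planned six.

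**Likely unit.** Teeth and implants come from the same six patients, so patient summaries would normally give six against six. Justifying g by unequal sample sizes points to a unit below the patient. The last step described before analysis is the location mean of three replicates. Pooling of locations or teeth is thus the likeliest reading, but it remains an inference.

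**Assumptions.** No intraclass correlation is given. Let s be the patient share of total variance, taken as .05/.10/.20, with six patients and normal values.

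**Pooled implant sites (18 per patient, n = 108).** Let L be the share of variance due to fixed differences between the 18 locations, which recur in every patient.
- True variance of the mean: s/6 + (1 − s − L)/108 = (1 + 17s − L)/108. The naive variance is about 1/108, so the ratio is DE = 1 + 17s − L.
- Approximate coverage of a nominal 95% interval: 2Φ(1.96/√DE) − 1.

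| s | DE, L = 0 | Coverage | DE, L = .5 | Coverage |
|---|---|---|---|---|
| .02 | 1.34 | 91% | 0.84 | 97% |
| .05 | 1.85 | 85% | 1.35 | 91% |
| .10 | 2.70 | 77% | 2.20 | 81% |
| .20 | 4.40 | 65% | 3.90 | 68% |

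Simulation gives 85/77/64% (L = 0) and 91/81/67% (L = .5) at s = .05/.10/.20. At L = 0 the 108 values carry the information of 108/DE = 58/40/25 independent ones. The interval is too narrow when DE > 1, that is when s > L/17; for L = .5 this is s > .029.

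**Averaging to tooth means first (4 × 6 = 24).** Take six sites per tooth and a tooth-within-patient share T. The correlation of tooth means is s / (s + T + (1 − s − T)/6), and DE = 1 + 3 × that correlation.
- T = 0: correlation .24/.40/.60, DE 1.72/2.20/2.80, simulated coverage about 87/81/74%.
- T = .20: correlation .13/.24/.40, DE 1.40/1.72/2.20, simulated coverage about 91/87/81%.

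**Single locations.** A tooth location over 24 teeth has DE = 1 + 3s = 1.15/1.30/1.60, with coverage about 93/92/88%. A single peri-implant location has one value per patient and keeps about 95%.

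**Tooth versus implant.** Simulated with 24 tooth and 18 implant values per patient and no true difference (two-sided 5% Mann-Whitney; nominal 95% interval for g):
- Patient effect specific to each tissue: false positives about 16/25/38%; coverage for g about 83/74/62%.
- Patient effect fully shared by both tissues: false positives 3–5%; coverage for g 96–97%.

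The 24 tooth values per patient (4 teeth × 6) are nominal. The 304 tooth comparisons exceed 4 × 12 × 6 = 288, so they must include more than these sites; some areas may also have been excluded, and no hard/soft split is given.

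**The case against.** The strongest reply has four parts.

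**Locations are fixed, not exchangeable.** The same sites recur in every patient. Differences between them inflate the naive standard deviation without adding uncertainty to the overall mean. This stands. A reader might infer that any positive within-patient correlation makes every pooled interval too narrow; that does not follow. With half the variance between locations and s = .02, the pooled interval covers about 97% and is slightly too wide. The shortfall reappears at .05 and is little changed at .20. Tooth-to-tooth variance softens the tooth-mean figures in the same way.

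**Pooling is never stated.** The intervals are called descriptive, and section 2.4 lists named locations. If reporting is per location, peri-implant intervals are sound and tooth intervals lose only a few points. This stands as a limit on the size of the problem. It does not supply the missing unit, and it sits awkwardly with the reason given for using Hedges' g.

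**The tests themselves may not be anti-conservative.** A reader might infer inflated false positives for tooth versus implant. The documents do not support a direction, because nothing shows whether patient effects are shared or tissue-specific.

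**Replicates.** A reader might also suspect that the three replicates are counted as separate observations. They are not: they are averaged first.

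If the patient was in fact the unit, unpaired tests would still ignore that teeth and implants share patients. No reading makes the listed methods fit the design.

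**Conclusion.** The concern holds and must be fixed. The plan names only independent-data methods for values nested in six patients, and it leaves both the unit and the tested contrasts unstated. Confidence is high in that omission and lower in its size.

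For pooled sites or tooth means, intervals for mean RMS are too narrow unless within-patient correlation is very small relative to fixed location differences. The coverage figures are illustrations: they rest on assumed variance shares, normal values and pooling, none of which the documents state. For tooth versus implant, the conclusion is only that the error rate is not controlled and may lie on either side of nominal. No general claim about power is made.

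A reader might go on to judge mean RMS against the 500 µm margin in section 2.5. The text does not support that step without further justification: the margin is set for a difference in means, whereas RMS is a non-negative magnitude of deviation.

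**What to change.** State the patient as the unit of inference, and say which contrasts the tests address. Then replace the independent-data analysis with one of two options; the choice between them is a matter of preference.

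1. **Per-patient summaries.** Average RMS per patient over the assessed locations, separately for tooth hard tissue, tooth soft tissue and peri-implant mucosa. Report each mean with a t-based 95% interval (5 df). Compare tissues by within-patient differences with a paired Hedges' g, and use Bonferroni across tissue pairs in place of Kruskal-Wallis.
2. **Mixed model.** Location fixed; patient, patient-by-tissue and tooth within patient random; small-sample degrees of freedom. This also helps where excluded areas leave patients with unequal sets of locations.

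Report per-location results descriptively, with numbers of patients and sites. Do not read mean RMS against 500 µm without a separate justification.

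The cost is SAP wording and a reanalysis of existing data. Intervals widen: for the implant mean with no location variance, the ratio of the patient-level to the pooled half-width is 2.571 × √[(s + (1 − s)/18)/6] / (1.982 × √(1/108)) = 1.76/2.13/2.72 at s = .05/.10/.20. Fewer results will probably be significant, and either option's assumptions rest on six patients. A rank-based paired test is a limited escape: with six pairs the smallest two-sided signed-rank P is 2/2⁶ = 0.031, which becomes 0.0625 or 0.094 after Bonferroni for two or three comparisons.

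### Section 2.5 adjusts multiple comparisons by single-step Bonferroni, which is valid but never more powerful than Holm's step-down at the same family-wise error

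*Combined protocol and SAP*

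**What the plan says.** Section 2.5 sets the testing level ("The level of significance was set at .05") and states that "the nonparametric Mann-Whitney U and Kruskal-Wallis tests were used to compare RMS between methods in hard and soft tissues". Its only multiplicity rule is "When performing multiple comparisons, the P-value was adjusted according to the Bonferroni Correction method".

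The section does not say which comparisons form a family, how many there are, or which pairwise procedure follows a Kruskal-Wallis test. The 95% intervals planned for the means and for Hedges' g are not described as adjusted for multiplicity.

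Section 2.4 describes the peri-implant measurement grid as "corresponding to 18 locations per patient, amounting to a total of 108" measurements. The three replicates at each location are averaged, so each location has one value per patient.

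**The concern.** Bonferroni compares every P-value in a family of m with .05/m. Holm compares the smallest with .05/m, the next with .05/(m-1), and so on up to .05, stopping at the first failure. Both hold the family-wise error at .05 whatever the dependence between the tests. Every Holm threshold is at least as large as Bonferroni's, so Holm can only add rejections.

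Bonferroni is often kept because it gives simple simultaneous intervals that agree with the tests. This plan uses no such intervals, so nothing is gained in return for the lost power. In a study sized on the statement that "at least six patients would be needed", power for differences between tissues is scarce. Some comparisons could be reported as non-significant that an equally strict procedure would have declared.

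**Working it through.** **Inputs.** Level .05, Bonferroni, Mann-Whitney and Kruskal-Wallis tests (section 2.5); 18 peri-implant locations and 108 measurements (section 2.4). The multiplicity sentence contains no figure to reproduce. The grid does: 108/18 = 6 values per location, in line with six patients.

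**Assumptions.** The plan gives no standard deviation or expected effect for these tests. I therefore assume m = 3 (for example tooth hard tissue, tooth soft tissue, peri-implant mucosa), normal test statistics, two-sided tests, and 60% power for each real effect at .05/3 = .0167.

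**1. Power at each Holm threshold.** The critical values at .0167, .025 and .05 are 2.394, 2.241 and 1.960. The shift giving 60% power at the first is 2.394 + 0.253 = 2.647. Power is then .600 at .0167, .6576 at .025 and .7541 at .05. The increments are B = .6576 - .600 = .0576 and C = .7541 - .6576 = .0965.

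**2. Power for one real effect under Holm (independent tests).**

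Power = .600 + B × S1 + C × S2

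- S1 is the chance that at least one of the other two P-values is at or below .0167.
- S2 is the chance that both others are at or below .025 and at least one of them is at or below .0167.

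| Real effects among 3 | S1 | S2 | Holm power per real effect | Bonferroni |
|---|---|---|---|---|
| 3 | 1 - .4² = .840 | .6576² - .0576² = .4291 | .600 + .0484 + .0414 = 69.0% | 60% |
| 2 | 1 - .4 × .9833 = .6067 | .6576 × .025 - .0576 × .0083 = .0160 | .600 + .0349 + .0015 = 63.6% | 60% |
| 1 | 1 - .9833² = .0331 | .025² - .0083² = .0006 | .600 + .0019 + .0001 = 60.2% | 60% |

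In simulation with a correlation of 0.5 between tests, the three Holm figures are about 68%, 63% and 60%.

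**3. Detecting all three real effects.** Under Bonferroni with independent tests the chance is .6³ = 22%. Under Holm it is .6576³ - .0576³ + 3 × .0965 × (.6576² - .0576²) = .2842 + .1242 = 41%. At a correlation of 0.5 the simulated figures are 35% and 52%.

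**4. A larger family.** With 15 comparisons (the six mucosal sides, 6 × 5/2), all effects real and 60% power each at .05/15, simulated average power rises from 60% to 72-74%.

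**5. How the adjustments differ (illustrative P-values).** Take raw values .012, .020 and .040.

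- Bonferroni: × 3 gives .036, .060, .120; one is below .05.
- Holm: .012 × 3 = .036; .020 × 2 = .040; .040 × 1 = .040; all three are below .05.

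**6. Where Holm gains nothing.** Its first threshold is also .05/m. Suppose all pairs of the 18 locations were compared by separate 6 v 6 Mann-Whitney tests. Then m = 18 × 17/2 = 153 and .05/153 = .00033, while the smallest exact two-sided P is 2/924 = .0022. Neither method can reject. For a family of 18 separate 6 v 6 tests with three real shifts of 2 SD, simulated average power is 28.9% under both methods. With all 18 shifted by 3 SD it is 70.7% under Bonferroni and 95.5% under Holm.

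**The case against.** The case for leaving the plan alone is a fair one. Bonferroni is valid, conservative and stated. The three-comparison gain of 8 to 9 points assumes that every effect is real, and it nearly vanishes when only one is. Effect sizes and intervals are also planned, so conclusions need not rest on adjusted P-values alone. The document is written in the past tense, so relaxing an adjustment after P-values exist would be a post-hoc change. All of this stands. It limits the size of the point and affects how a change should be reported, but it gives no statistical advantage to Bonferroni.

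Holm's extra rejections do use error allowance that Bonferroni leaves idle. With two real effects and one true null, Bonferroni tests the null at .0167, while Holm may test it at up to .05. The family-wise error still stays within .05.

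A reader might also infer that Bonferroni makes significance at single peri-implant locations close to unattainable. The documents do not support that, for three reasons.

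- Nowhere does the plan say that all 153 pairs of locations are tested, or that separate 6 v 6 Mann-Whitney tests are run.
- Other readings of the same sentence can reach significance. With pooled-rank comparisons after Kruskal-Wallis, the standard error of a mean-rank difference is √(108 × 109/12 × 2/6) = 18.1. The largest possible gap of 102 gives z = 5.64 and P = 1.7 × 10⁻⁸, well below .00033. Pooled by side (18 values each), the smallest exact Mann-Whitney P is 2.2 × 10⁻¹⁰ against .05/15 = .0033.
- Where significance really is out of reach, six values per location and the number of tests are the cause, and Holm does not cure it.

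**Conclusion.** The concern holds as a modest matter of efficiency. Bonferroni as stated is valid; Holm is at least as powerful in every case, at the same family-wise error and with no added assumption.

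For three comparisons with an assumed 60% power each at .05/3, the gain in average power is about 8 to 9 points if all effects are real, 3 to 4 points if two are, and almost nothing if one is. It is zero when no P-value passes .05/m and never negative. These figures rest on normal test statistics, correlations between 0 and 0.5, and an assumed family of three, because the plan does not define its families.

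Both methods take the raw P-values as valid. The named tests do not account for several locations measured in the same patient, and changing the adjustment does not correct that.

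**What to change.** In section 2.5, replace the Bonferroni method by 'Holm step-down adjustment, applied within each family of pairwise comparisons'.

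The cost is one sentence. The calculation can be done by hand from the raw P-values: sort them in ascending order, multiply by m, m-1, ..., 1, never let an adjusted value fall below the one before it, and cap at 1. Simple matching simultaneous intervals are given up, but the plan does not use them.

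If the P-values have already been computed, report the change as made after the fact and show the Bonferroni results beside the Holm results.

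### The tooth-versus-implant contrast rests on a labelled Hedges' g with no stated unit and no allowance for clustering within six patients; a within-patient difference in µm would be sounder

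*Combined protocol and SAP*

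**What the plan says.** Section 2.5 of the combined protocol and SAP defines the contrast between soft tissue around teeth and around the implant as a standardised effect: "measurements (tooth vs implants) was calculated as" Hedges' g with a 95% confidence interval. The choice of g is justified by the two groups having different sizes. The value is then classified: "Effect size was considered as small (<0.3), moderate" from 0.3 to 0.8, and large from 0.8 upward. Nothing links the label to the confidence interval, so the label follows the point value.

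The same section plans means with 95% confidence intervals for the studied parameters, so RMS in each tissue will also appear in native units. It does not name a tooth-minus-implant difference in µm, with or without an interval.

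On numbers, section 2.5 says "at least six patients would be needed". Section 2.4 describes the periimplant sites as "corresponding to 18 locations per patient, amounting to a total of 108" measurements. Section 2.4 also lists six soft-tissue locations per tooth on four teeth, in the same mouths as the implants. The plan does not say whether g is computed on sites or on patients, and it describes no method for sites nested in patients or for tooth and implant sharing a mouth.

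**The concern.** RMS deviation already has a natural unit, and a reader wants to know how many µm worse, if at all, the digital scan reproduces periimplant mucosa than tooth gingiva. A ratio to the sample SD, reduced to one of three words, hides that. The same label can stand for very different distances. Large begins at 0.8 × SD, which is 40 µm at an assumed SD of 50 µm and 400 µm at an assumed SD of 500 µm. The plan states no SD.

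The statistical problem is more serious. If g treats every site as independent, its standard error reflects more than a hundred sites per group when only six patients vary independently. The label then crosses the cut-offs by chance more often than it appears to, and the published interval is too narrow to warn the reader. If g is computed per patient, the interval is honest about there being six patients (apart from ignoring pairing), but the label is then very unstable.

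**Working it through.** **Inputs.** Patients: 108/18 = 6, which agrees with the stated minimum. Implant sites: 108 (section 2.4). Tooth soft-tissue sites: not stated separately, because the 304 tooth comparisons in section 2.4 are not split into hard and soft tissue. I assume the full grid, 4 teeth × 6 locations × 6 patients = 144. ICC and within-mouth correlation: not given, so shown as ranges. Cut-offs: 0.3 and 0.8 (section 2.5).

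**1. Sites as the unit, taken as independent.** SE(g) at g = 0 is √(1/108 + 1/144) = √0.0162 = 0.127, and 1.96 × 0.127 = 0.25. With no true difference, P(|g| ≥ 0.3) is about 2%. If independence held, the labels would behave well.

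**2. Sites as the unit, clustered in patients.** Let the ICC be the share of total variance due to patient, and let s be the fraction of the patient effect common to tooth and implant in the same mouth. In units of the total SD, the difference in means has variance

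2 × ICC × (1 − s)/6 + (1 − ICC) × 0.0162.

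At ICC 0.3:
- s = 0: 0.100 + 0.0113 = 0.111, SD 0.334.
- s = 0.5: 0.050 + 0.0113 = 0.061, SD 0.248.

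The naive standard error is still about 0.127, so the true spread is roughly two to two and a half times what the interval assumes. Simulation with normal data and no true difference gives the figures below. Each range runs between s = 0.5 and s = 0.

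| ICC | Labelled moderate or large | Coverage of nominal 95% CI |
|---|---|---|
| 0 | about 2% | about 95% |
| 0.1 | 9–17% | 75–84% |
| 0.3 | 24–38% | 53–68% |
| 0.5 | 35–50% | 44–56% |

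The formula also marks the limit of the argument. If the patient effect were wholly shared (s = 1), the first term would vanish and the naive interval would not be too narrow.

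**3. Patients as the unit, 6 against 6.** With 10 degrees of freedom the correction is J = 1 − 3/39 = 0.923, and g = J × t × √(1/6 + 1/6). The cut-offs correspond to |t| = 0.3/(0.923 × 0.577) = 0.563 and 0.8/(0.923 × 0.577) = 1.501. With no true difference and zero within-mouth correlation, P(|t| > 0.563) = 59% (moderate or large) and P(|t| > 1.501) = 16% (large). The 95% half-width at g = 0 is 1.96 × √(12/36) = 1.13, against a gap of 0.5 between the cut-offs. Simulating paired values with the same formula for g, the 59% falls to 52% at correlation 0.3, 45% at 0.5 and 34% at 0.7; the 16% falls to 10%, 6% and 3%.

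**4. The alternative.** Take each patient's mean tooth RMS minus mean implant RMS and form a one-sample t interval on 5 degrees of freedom. In the same simulations its coverage stays at about 95% at every ICC tried (0 to 0.8). Its half-width is 2.571 × SD of the six differences/√6, or 1.05 of those SDs. At ICC 0.3 that is about 2.571 × 0.248 = 0.64 to 2.571 × 0.334 = 0.86 of a total SD, against the nominal 0.25 of the site-level interval.

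**The case against.** The plan does more than attach a label. It reports g with a 95% CI and reports means with 95% CIs. A reader might infer that the label is the only evidence on this contrast; the documents do not support that. Moreover, no test or decision rule depends on the label, and the primary outcomes concern the deviation between impression methods.

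A reader might also infer that the labels are mostly noise. That is not established. The per-patient figure of 59% is for independent groups, whereas tooth and implant share a mouth, and the stated reason for choosing g points away from per-patient analysis, which would give equal groups. At site level the rate depends on an ICC that the documents do not give, and it is only about 2% if sites are independent.

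Finally, a reader might infer that the labels contradict the plan's own µm limits. They do not. The 500 µm margin belongs to the sample-size statement about "the limits of a two-sided 90% confidence interval" for the difference between methods. The band described by "the best results ranging between +100 and -100" µm is a colour setting for signed deviations on the map. Neither was set for a tooth-minus-implant difference in RMS.

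These objections stand and narrow the point. They do not remove it. The planned CI is reassuring only if it is valid, and under site-level analysis with clustering it is not. Separate group means with separate intervals do not give the interval for a within-mouth difference.

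**Conclusion.** The concern holds in a limited form. The contrast is expressed as a standardised effect with an unstated unit, no described allowance for clustering, and a size label taken from the point value; the direct difference in µm is missing. On the more likely site-level reading, a modest ICC of 0.1 to 0.3 would put 9–38% of null trials in the moderate or large category and reduce coverage of the 95% CI to 53–84%. On the per-patient reading, the null label rate is 59% at zero within-mouth correlation and 45% at 0.5.

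These figures assume 144 tooth soft-tissue sites, normally distributed values, equal variances, and a patient effect shared between tooth and implant by no more than half. They would be smaller with more sharing. The plan's text is not in conflict with itself here. This is a choice of summary that should be improved, and it does not undermine the primary comparison of methods.

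**What to change.** In section 2.5, make the reported contrast the within-patient tooth-minus-implant difference in mean RMS, in µm, with a 95% CI that takes the patient as the unit: a paired t interval on six differences, or a mixed model with a patient effect. Keep g as a supplementary figure, and state whether it is computed on patients or on sites. Drop the size labels, or apply one only when the whole CI lies within that category. Do not read the contrast against the 500 µm margin or the ±100 µm colour band as formal limits; if a limit is wanted, it must be set and justified for this contrast.

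The cost is a few lines of SAP wording and one row in the results table, since the measurements already exist. The interval will be visibly wider and the familiar label will be lost.
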